Aim 2a: To obtain preliminary data on caregiver intermediate (self-efficacy for (a) coping with cancer and (b) abbreviated progressive muscle relaxation) and outcome variables (burden, psychological distress, quality of life) in intervention caregivers and waitlist control caregivers at the start of radiation (T1), end of radiation (T2), and 6-weeks post-radiation (T3).

Aim 2b: To compare intermediate (self-efficacy for (a) coping with cancer and (b) abbreviated progressive muscle relaxation) and outcome variables (burden, psychological distress, quality of life) between intervention caregivers and waitlist control caregivers at T1, T2, and T3.

Hypothesis: (Aim 2a) *Intermediate and outcome variables will improve in intervention caregivers post-intervention compared to pre-intervention and (Aim 2b) intervention caregivers will have better intermediate (higher self-efficacy for a) coping with cancer, and b) abbreviated progressive muscle relaxation) and outcome variables (less burden, less psychological distress, higher QOL) at T2 compared to waitlist control caregivers.*

Aim 3: To obtain preliminary data on caregiver cortisol response (cortisol slope, cortisol awakening response, area under the curve, and intra-individual cortisol variability) at T1 – T3 in intervention caregivers and waitlist control caregivers.

Hypothesis: *Intervention caregivers will demonstrate a more normal (steeper) diurnal cortisol rhythm (slope) at T2 compared to waitlist control caregivers.*

Aim 4: To refine intervention procedures and materials for future studies by examining: a) qualitative data from caregivers and interventionist notes and b) quantitative data regarding module utilization.

Methods and Measures

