Design: Recruitment will include both patients and caregivers, although patients are not receiving the intervention. We will recruit 40 caregivers (20 intervention caregivers; 20 waitlist control caregivers) of patients with head and neck cancer (HNC) referred for radiotherapy (RT) and their informal caregivers, before or at the start of patient RT. After baseline assessment, caregivers will be randomized at the time of registration using a randomization scheme uploaded into the registration system. The randomization scheme will be developed by the statistician. Block sizes will be chosen randomly to ensure that future assignments cannot be inferred from previous ones. Caregivers will be randomized to receive either a psycho-educational and stress management skills building intervention offered in a SSM format, accessible in hard copy and online, with iPads linking to study materials available during daily patient RT sessions, or a waitlist control group. Caregivers will complete assessments at the start of RT (T1), end of RT (T2), and 6-weeks post-RT (T3). Waitlist control caregivers will be offered *Prepare to Care* materials (without support from the study interventionist) after final assessment at T3. Patient participation is optional and restricted to providing consent for study staff to abstract information on clinical information from their medical record. If a patient declines to participate in the study, caregivers will be asked to report the patient clinical information collected at T1. See Appendix A for study schema.

Setting: Participants will be recruited from the outpatient radiation clinics at the Comprehensive Cancer Center of Wake Forest University and the Lexington Medical Center or by mail. Participants will meet with the study interventionist at the radiation clinic or by telephone, and have the option to access intervention materials from the study website using i-Pads that remain at the clinic or accessing the website away from the clinic. The self-management intervention is designed so that caregivers can utilize the kit in a preferred location (e.g., at home) and time.

Subjects selection criteria

Caregivers

- **Inclusion Criteria**

(1) providing the majority of the informal (unpaid) care during RT for a patient meeting inclusion criteria (see below) and participating in study, and (2) ≥ 18 years of age.

- **Exclusion Criteria**

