(1) has a current cancer diagnosis, (2) cannot read/ communicate in English, (3) Caregivers who have an endocrine disorder (e.g., diabetes and thyroid disorders), or is currently taking a steroid-based medication will not be eligible to participate in the saliva portion of the study.

Care-recipients

- **Inclusion Criteria**

(1) has a new or recurrent AJCC stage I-IV squamous cell carcinoma of the upper aerodigestive tract (including lip/oral cavity, nasopharynx, salivary gland, oropharynx, hypopharynx, paranasal sinus, and larynx cancers), (2) has planned external beam radiotherapy (+/- chemotherapy) for 6-7 weeks, (3) ≥ 18 years of age, and (4) has an informal (unpaid) caregiver during RT who is participating in study.

- **Exclusion Criteria**

(1) cannot read/ communicate in English.

- **Sample Size**

The sample size is based on feasibility (Aim 1). Our primary feasibility measures are participation and retention rates. About 110 patients present to our outpatient radiation clinic for treatment per year (9/mo). Based on previous experience, we expect approximately 75% of patients (n = 82) will have a caregiver and at least 75 patient-caregiver dyads will meet eligibility criteria (6/mo). With an estimated participation rate (consistent with PI's experience) of 70%, we expect to recruit 40 patient-caregiver dyads within 8-10 months. If we approach 56 participants to recruit 40, we will be able to estimate the participation rate within +/- 12% using a two-sided 95% confidence interval; thus, we can be 95% confident that the true recruitment rate would be between 59% and 83%, which would support that the study is feasible. With 40 participants we can estimate the retention rate within +/- 12%. If the observed retention rate is 80%, we can be 95% confident that the true rate is between 67% and 92%, which would indicate a feasible study.

Interventions and Interactions

After recruitment and randomization, caregivers in the intervention group will meet with the study interventionist to review the intervention.

Overview of Intervention (see Table 1)

The multi-component intervention (or kit), *Prepare to Care*, includes:

- 1) brief introduction video on a DVD,
- 2) binder including eight workbook modules offered in hard copy, and
- 3) CD with audio instructions to facilitate Progressive Muscle Relaxation (PMR) Training (included in module 8).

Modules

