Intermediate Outcomes		
Self-efficacy in coping with cancer Caregiver Inventory (CI)[47]	T1; T2; T3	21-item instrument assessing caregivers' perceived self-efficacy for coping with cancer (managing medical information, caring for care recipient, caring for oneself, managing difficult interactions/emotions); demonstrated validity and reliability.
Self-efficacy in PMR	T1; T2; T3	3-item instrument developed for study to evaluate self-efficacy in PMR.
Outcome Variables		
(CES-D) [48]	T1; T2; T3	20-item instrument how often over the past week they experienced symptoms associated with depression, such as restless sleep, poor appetite, and feeling lonely. The CESD has been widely used in caregiver populations.
(PROMIS Emotional Distress Anxiety Short Form- 8a)[49]	T1; T2; T3	Brief 8-item assessment of anxiety over the past week.
Caregiver burden • Caregiver Reaction Assessment (CRA) [50]	T1; T2; T3	24-item instrument assessing positive and negative aspects of caregiving (esteem, lack of family support, finances, schedule, and health). The CRA has been tested in cancer caregivers; demonstrated validity and reliability [50, 51].
QOL • Caregiver Quality of Life Index-Cancer (Cqol-Canc) [52]	T1; T2; T3	35-item instrument assessing dimensions of caregiver QOL (burden, disruptiveness, positive adaptation, financial concerns). The Cqol-Canc has demonstrated validity and reliability [51, 52].
Aim 3		
Salivary Cortisol Collection (for eligible caregivers only)	T1; T2; T3	Collected three times a day (at awakening, 30 minutes post-awakening, and bedtime) for two consecutive days following T1, T2, and T3. Saliva samples are collected by placing a cotton roll under the tongue for approximately 1-2 minutes which is subsequently stored in a plastic tube and refrigerated.
Aim 4		
Modules Utilized (intervention caregivers only)	Study duration	Frequency of intervention modules utilized; retrieved from caregiver logs
Interventionist notes	Study duration	Process notes regarding intervention implementation

Analytical Plan

The analyses will provide quantitative data on participation, retention, and accrual, and estimates of the effect size of the intervention for intermediate and outcome variables. This information, along with ratings of acceptability and qualitative analyses, will allow us to refine the protocol for a larger study.

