Aim 1: To assess feasibility (accrual, participation, and retention) and acceptability of a supported self-management intervention for psycho-education and stress management skills building designed for

informal caregivers (Intervention Group, n=20; Waitlist Control Group, n=20) of HNC patients undergoing RT.

Accrual rate will be defined as the number of caregivers who agreed to participate divided by the number of months of recruitment. Participation rate will be defined as the percent of eligible participants who agreed to participate. Retention rate will be defined as the number of participants who completed T3 measures divided by the number who consented to participate. Mean accrual rate, participation rate, and retention rates and their associated 95% confidence intervals (CI) will be estimated.

Acceptability will be summarized quantitatively and qualitatively. Descriptive statistics will summarize participants' overall rating of acceptability; ANOVA and regression models will examine if acceptability varies by demographic, caregiving, or patient characteristics. A codebook for analyzing the qualitative interviews will be developed using a thematic analysis procedure, facilitating coding into discrete categories. Interviews will be coded by at least two raters and discrepancies will be discussed until consensus is reached. Frequency counts will be calculated for themes pertinent to caregivers' likes/dislikes.

Aim 2a: To obtain preliminary data on caregiver intermediate (self-efficacy for (a) coping with cancer and (b) abbreviated progressive muscle relaxation) and outcome variables (burden, psychological distress, quality of life) in intervention caregivers and waitlist control caregivers at the start of radiation (T1), end of radiation (T2), and 6-weeks post-radiation (T3).

Aim 2b: To compare intermediate (self-efficacy for (a) coping with cancer and (b) abbreviated progressive muscle relaxation) and outcome variables (burden, psychological distress, quality of life) between intervention caregivers and waitlist control caregivers at T1, T2, and T3.

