We will use a mixed effects model with a random subject effect and time (T1,T2,T3), group, and a group by time interaction to model change in the intermediate variables (self-efficacy for (a) coping with cancer (CI) and (b) PMR) and outcome variables (burden (CRA), depression (CESD), anxiety (PROMIS Short Form-Anxiety 7a), and QOL (CQoL-Canc), by group from T1 to T2 to T3). We will use linear contrasts to compare the intervention to the control group at T1, T2, and T3. In exploratory analyses we will model the relationship between each outcome and the intermediate variable, by including the intermediate variable as a fixed effect in the model. These results are exploratory due to concurrent measurement with outcome variables; in future studies we would capture potential mediators at an intermediate time point.

Aim 3: To obtain preliminary data on caregiver cortisol response (cortisol slope, cortisol awakening response, area under the curve, and intra-individual cortisol variability) at T1 – T3 in intervention caregivers and waitlist control caregivers.

Analysis Plan: Analyses for Aim 3 will be conducted using data from caregivers who were not excluded from the saliva portion of the study. Several summary measures will be derived from the three daily cortisol values, including the mean levels at each time, the mean cortisol awakening response (CAR – change in cortisol from awakening to 30 minutes), the area under the curve (AUC), the diurnal slope (change in cortisol between awakening and bedtime), and the intraindividual cortisol variability, which will be estimated using the methods as described in Sannes et al.[53] to assess group differences in cortisol parameters. We will use a mixed model to evaluate differences between the groups in these parameters at times T1 and T2 and T3. For a subset of the sample who completed measures on intermediate and outcome variables and cortisol, in exploratory models, we will include the cortisol summary measures as predictor variables in the models described for Aim 2 above.

Aim 4: To refine intervention procedures and materials for future studies by examining: a) qualitative data from caregivers and interventionist notes and b) quantitative data regarding module utilization.

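### The Aim 2b contrasts at T2 and T3 are valid but inefficient: they leave out the T1 questionnaire score taken before randomisation, and the arms are also compared at T1

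*Combined protocol and SAP*

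**What the plan says.** The Analytical Plan for Aims 2a and 2b specifies a "mixed effects model with a random subject effect and time (T1,T2,T3), group, and a group by time interaction" for each intermediate and outcome questionnaire. T1, T2 and T3 are all responses in this model. The between-arm comparison is then named: "We will use linear contrasts to compare the intervention to the control group at T1, T2, and T3". Aim 2b is worded the same way, as a comparison "between intervention caregivers and waitlist control caregivers at T1, T2, and T3". The hypothesis under Objectives is narrower and concerns "outcome variables (less burden, less psychological distress, higher QOL) at T2 compared to waitlist control caregivers".

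On timing, the Design section says: "After baseline assessment, caregivers will be randomized at the time of registration". T1 is the only baseline assessment listed. Neither the Design section nor the Analytical Plan enters T1 as a covariate or gives the arms a common T1 mean.

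The Analytical Plan expects the analyses to give "estimates of the effect size of the intervention for intermediate and outcome variables", to help refine the protocol for a larger study. The Sample Size section rests N = 40 on the precision of the participation and retention rates. No alpha, power or target precision is attached to Aim 2.

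**The concern.** A random subject effect is easily mistaken for baseline adjustment. When the group effect is free at every visit, the model estimates six separate cell means. With complete data, the T2 contrast is then the difference between two of them, whatever happened at T1. A pre-randomisation measurement of the same scale is therefore left out of the comparison that carries the hypothesis.

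This has two consequences. First, the T2 and T3 effect estimates are less precise than the data allow, and precision is what a 40-person pilot lacks. Second, in the one trial actually run, part of any chance T1 gap stays in the T2 estimate. The planned standard error already allows for this on average, so it is not bias and not a separate harm. It is the same lost precision seen from within a single trial.

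The T1 contrast is a smaller matter. If T1 precedes allocation, the arms can differ there only by chance, so comparing them says nothing about the intervention.

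**Working it through.** **Inputs.** From the documents: 20 caregivers per arm, randomisation after baseline assessment, and the same instruments at T1, T2 and T3. Assumed, because the documents give no values: a correlation rho between visits of 0.3 to 0.8, equal for all visit pairs, and unit variance at each visit (results in SD units).

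**The plan's own figures.** None is given for Aim 2b. The feasibility figures behind N = 40 reproduce: 40/56 = 71.4% ± 1.96·√(0.714·0.286/56) = ± 11.8 points, and 80% of 40 gives ± 1.96·√(0.8·0.2/40) = ± 12.4 points, against ± 12% stated for both. They do not bear on Aim 2.

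**Does the planned contrast use T1?** A random-intercept fit to simulated complete data gave a T2 contrast of −0.3573, and the raw T2 mean difference was also −0.3573. Adding 1 SD to every T1 score in one arm left the contrast and its standard error unchanged.

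**Three estimators.** Let D1 and D2 be the between-arm differences at T1 and T2, with n = 20 per arm and complete data.

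- Planned: D2, SE = √(2/n) = √0.1 = 0.316; 95% half-width 1.96 × 0.316 = 0.62.
- T1-adjusted (equal T1 means): D2 − rho·D1, SE = 0.316·√(1 − rho²).
- Difference in change: D2 − D1, SE = √(4(1 − rho)/n).

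| rho | Adjusted SE | Variance cut against planned | Adjusted half-width | Change SE | Change variance against planned |
|---|---|---|---|---|---|
| 0.3 | 0.302 | 9% | 0.59 | 0.374 | +40% |
| 0.5 | 0.274 | 25% | 0.54 | 0.316 | 0% |
| 0.6 | 0.253 | 36% | 0.50 | 0.283 | −20% |
| 0.7 | 0.226 | 49% | 0.44 | 0.245 | −40% |
| 0.8 | 0.190 | 64% | 0.37 | 0.200 | −60% |

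Estimating the adjustment costs about 1/(40 − 4) = 2.8% of variance. At rho 0.3 the net cut is 1 − 0.91 × 37/36 = 6.5%. To match the adjusted precision, the planned contrast would need 20/(1 − rho²) per arm: about 22, 27, 31, 39 and 56.

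**With dropout.** Assume 10% lost by T2 and 20% by T3. Per arm, 16 have all three visits, 2 have T1 and T2, and 2 have T1 only. Exact generalised least squares gives the following (cuts from unrounded SEs):

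| rho | T2 SE, planned to adjusted | Cut | T3 SE, planned to adjusted | Cut |
|---|---|---|---|---|
| 0.3 | 0.332 to 0.318 | 8% | 0.349 to 0.336 | 7% |
| 0.5 | 0.329 to 0.289 | 23% | 0.343 to 0.304 | 21% |
| 0.6 | 0.327 to 0.267 | 34% | 0.339 to 0.281 | 31% |
| 0.7 | 0.325 to 0.238 | 46% | 0.334 to 0.250 | 44% |
| 0.8 | 0.322 to 0.200 | 62% | 0.329 to 0.210 | 59% |

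With missing visits T1 does enter the planned contrast a little through the random effect, but most of the loss remains. A REML random-intercept simulation with the same dropout and no true effect agreed: T2 variance cuts of 8, 25, 35, 48 and 62%, and mean estimates within 0.004 SD of zero under both models.

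**Chance T1 gaps.** D1 has SE 0.316. For any one outcome, P(|D1| > 0.3 SD) = 2·[1 − Φ(0.949)] = 34% and P(|D1| > 0.5 SD) = 2·[1 − Φ(1.581)] = 11%. A 0.5 SD gap moves the planned T2 estimate by 0.5·rho: 0.15, 0.25, 0.30, 0.35 and 0.40 SD at the five values of rho.

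**The case against.** The strongest reply is that nothing is broken. The contrasts are unbiased with correct standard errors, the study is a feasibility pilot, and no stated decision turns on a half-width of 0.62 rather than 0.54 SD. That stands, and it limits how much this point matters. It does not remove the gain in estimates that the plan itself promises.

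A second reply is that the group-by-time term is there to model change, so the same fit already gives a T1-referenced comparison. Against that difference in change, adjustment cuts variance by (1 − rho)/2, which is only 15% at rho 0.7 and 10% at rho 0.8. Against the better of the two contrasts at each rho, the gain peaks at 25% (rho 0.5) and is 9% at rho 0.3. The arithmetic is right. But the plan names the per-visit contrast for Aim 2b, the difference in change is less precise than adjustment at every rho below 1, and choosing between the two after seeing data would not be prespecified.

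Third, rho is unknown, and T1 and T2 lie on either side of 6 to 7 weeks of radiotherapy. A low correlation cannot be ruled out, least of all for the "3-item instrument developed for study to evaluate self-efficacy in PMR", for which no stability data are given.

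Fourth, the plan speaks of comparing the arms at T1, not of a T1 test or p-value. That is fair, and a descriptive T1 table would satisfy the point.

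Finally, the Design section does not expressly equate the baseline assessment with T1. The natural reading does, but a sentence confirming it would be worthwhile.

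**Conclusion.** The concern holds, as a matter of efficiency and not of validity. As specified, the Aim 2b contrasts at T2 and T3 make almost no use of the T1 score. Using it would cut the variance of the T2 estimate by 9% to 64% with complete data, or 8% to 62% with the assumed dropout, for rho between 0.3 and 0.8. The small cost of estimating the adjustment comes off these figures.

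The size depends on rho, which the documents do not give. Calling the planned contrasts valid assumes that dropout is missing at random and that one common variance fits all visits. The case for adjustment rests on the T1 questionnaires preceding allocation, which is how the Design section reads. Even after adjustment the intervals are wide, and Aim 1 and its sample-size basis are unaffected. The change should be made because it is nearly free, not because the plan fails without it.

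**What to change.** For the Aim 2 questionnaires, keep the mixed model but constrain the T1 means to be equal across arms: time, plus group-by-T2 and group-by-T3 terms, with no group term at T1. This retains caregivers who have only T1 data. Modelling T2 and T3 with T1 as a covariate is a close alternative, but it drops those caregivers. A random intercept forces one common correlation on all visit pairs; an unstructured 3×3 covariance would avoid that.

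Report the T2 group term as the Aim 2b effect, and the T3 term likewise. Show T1 by arm descriptively, and reword Aim 2b under Objectives and in the Analytical Plan to match. Add a clause confirming that the T1 questionnaires are completed before allocation. Fix the choice before outcome data are examined.

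Do not extend the constraint to Aim 3 cortisol unless T1 saliva is confirmed to precede randomisation. The Salivary Cortisol section places collection on the two days after T1, so those samples may follow allocation.

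The cost is a sentence or two in the Analytical Plan and the matching Aim 2b wording. It needs no new data, software or participants.

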See Table 2 for the assessment plan. For caregivers, sociodemographics and caregiving characteristics will be collected at recruitment. We will collect basic demographics and patient clinical information via medical chart review at recruitment and after RT. At T1, T2 and T3, caregivers will complete instruments at the RT clinic (or by phone, mail, or email using REDCAP) to assess intermediate (self-efficacy in (a) coping with cancer and (b) PMR and outcome variables (burden, psychological distress, quality of life). Caregivers may also self-collect saliva samples (see additional details below). Between T2 and T3, we will assess intervention caregivers' overall acceptability of the intervention with a quantitative survey developed for the study and semi-structured interviews (lasting approximately 30 minutes to an hour) to explore factors influencing overall acceptability. Caregivers will be asked what they liked and disliked about content and delivery of intervention materials, weekly sessions with the interventionist, and email/text reminders. Interviews will be recorded and transcribed, and qualitative data will be managed using Microsoft Excel.

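### The exploratory Aim 2 and Aim 3 models enter a repeatedly measured predictor as one term, so its coefficient mixes between-caregiver and within-caregiver association and cannot be read as change tracking change

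*Combined protocol and SAP*

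**What the plan says.** The main Aim 2 analysis is a "mixed effects model with a random subject effect and time (T1,T2,T3), group, and a group by time interaction to model change" in the intermediate and outcome variables. The exploratory step takes that model and adds a predictor: "we will model the relationship between each outcome and the intermediate variable, by including the intermediate variable as a fixed effect in the model". The schedule makes the predictor time-varying: "At T1, T2 and T3, caregivers will complete instruments at the RT clinic", and Table 2 lists both self-efficacy measures and every outcome at all three visits.

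The plan states one limitation: "These results are exploratory due to concurrent measurement with outcome variables; in future studies we would capture potential mediators at an intermediate time point".

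Under Aim 3, for the subset with both kinds of data, "we will include the cortisol summary measures as predictor variables in the models described for Aim 2 above". Saliva is also collected at T1, T2 and T3.

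For these models the documents mention no centring on the caregiver's mean, no separate between-caregiver term, no baseline adjustment and no change scores. They do not say which association the coefficient represents.

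**The concern.** A predictor that varies over visits carries two kinds of information. Between caregivers, those who are generally more confident may be generally less distressed. Within a caregiver, distress may fall at the visits where confidence is higher. A random intercept gives the first less weight but does not remove it.

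The plan uses the neutral word 'relationship' for this step. It also builds the model to describe change, hypothesises under Aim 2a that caregivers improve from before to after the intervention, and speaks of capturing potential mediators in later work. A reader will therefore be inclined to take the coefficient as a link between change in self-efficacy and change in outcome. Stable differences between caregivers could produce such a coefficient with no link of that kind. They could also mask or inflate a link that does exist. Accepting concurrent measurement does not help, because that caveat is about which variable comes first.

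**Working it through.** **The plan's own figures.** None is given for these models. The only design precision is for Aim 1, and it reproduces apart from rounding: 40 of 56 gives 1.96 × √(0.714 × 0.286/56) = 11.8 points, and 80% of 40 gives 1.96 × √(0.8 × 0.2/40) = 12.4 points, against a stated 12. It does not bear on this point.

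**Inputs from the documents.** 40 caregivers, 20 per arm; three visits; random subject effect; fixed time, group and group by time; predictor entered once. A count of 32 follows from the 80% retention example under Sample Size (0.8 × 40).

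**Assumptions.** The documents give no intraclass correlations (ICCs), slopes or correlations, and no significance level for these models. I use a unit-variance predictor with ICC 0.5 to 0.7, a range of outcome ICCs and between-caregiver slopes, and two-sided 5%.

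**Step 1: what the coefficient estimates.** On balanced data with T visits, ignoring the other fixed effects,

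b = [S_W·b_W + (1−θ)²·S_B·b_B] / [S_W + (1−θ)²·S_B], with θ = 1 − 1/√(1 + T·var_u/var_e).

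S_W and S_B are the within- and between-caregiver sums of squares of the predictor, b_W and b_B the two slopes, and var_u and var_e the subject and residual variances of the outcome.

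**Step 2: one case by hand.** Predictor ICC 0.5, residual outcome ICC 0.5, T = 3, within-slope 0, slope on stable levels −0.6.

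- θ = 1 − 1/√(1 + 3 × 1) = 0.5, so (1−θ)² = 0.25.
- Per caregiver, S_W = 2 × 0.5 = 1.0 and S_B = 3 × (0.5 + 0.5/3) = 2.0.
- Weight on the between slope: 0.25 × 2.0 / (1.0 + 0.25 × 2.0) = 1/3.
- Slope on observed means: −0.6 × 0.5 / (0.5 + 0.5/3) = −0.45.
- Blended coefficient: −0.45/3 = −0.15, although the within-slope is 0.

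Simulation of the stated model (REML, 600 runs) gives −0.14, with p<0.05 in 32% of samples. The within-caregiver term of the split model averages 0.005 and is significant in 4%.

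**Step 3: range with no within-caregiver link, 40 caregivers.** ICC pairs are predictor/outcome.

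| Assumed between-caregiver association | Planned coefficient | p<0.05 |
|---|---|---|
| None (stable levels uncorrelated) | about 0.00 | about 6% |
| Slope −0.3, ICCs 0.5/0.5 and 0.6/0.6 | not tabulated | 10% to 12% |
| Slope −0.3, ICCs 0.7/0.3 | not tabulated | 34% |
| Slope −0.6, predictor ICC 0.5–0.7, residual outcome ICC 0.3–0.7 | −0.08 to −0.32 | 17% to 78% |

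The within-term of the split model, run for the −0.6 row, averages 0.00 and is significant in 4% to 7%. The −0.3 rows cover three ICC pairs only, so they are not the limits for that slope.

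A second set of runs (2,000 per setting) is indexed by the correlation of stable levels. At ICCs 0.6/0.6, correlations of −0.3, −0.5 and −0.7 give coefficients −0.08, −0.15 and −0.23, significant in 15%, 36% and 65%. Over all ICC pairs tried (0.5 to 0.7) and these correlations, the rate is 11% to 83% with 40 caregivers and 9% to 74% with 32. The between slope carries about 20% to 58% of the weight. The within-term of the split model is significant in 5.4% to 5.6%.

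**Step 4: a real within-caregiver link of −0.30** (ICCs 0.6/0.6, 40 caregivers). The single coefficient averages −0.22, −0.36 or −0.14 for stable-level correlations of 0, −0.5 or +0.3. The within-term of the split model averages −0.30 each time, so the distortion can go either way.

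**Step 5: what splitting costs.** With equal slopes, the within-term's standard error is about 1.1 to 1.7 times that of the single coefficient. Root mean squared error about a true within-slope of −0.2 (ICCs 0.6/0.6), single versus split: 0.097 versus 0.116 at a between slope of −0.3; 0.118 versus 0.121 at −0.4; 0.142 versus 0.113 at −0.6. Power of the within-term to detect −0.2 is about 43%.

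**The case against.** The best defence is that the plan promises only a relationship, and a random-intercept coefficient is a legitimate if mixed summary of one. If confident caregivers are in general less distressed, that association is real. The analysis is labelled exploratory, with a stated limit on causal reading. This stands, and it rules out four stronger readings that a reader might infer:

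- *That the plan commits itself to a mediation or change-on-change result.* It does not. Mediators appear only in a clause about later work: "in future studies we would capture potential mediators at an intermediate time point".
- *That cortisol is treated as a mediator.* The Aim 3 text calls the cortisol summaries predictors and nothing more.
- *That this coefficient will steer the larger study.* The opening of the Analytical Plan names feasibility measures, intervention effect sizes, acceptability and qualitative work. The Aim 4 text speaks broadly of synthesising findings, but the refinements it lists concern recruitment, materials, delivery and reminders. No stated decision turns on this coefficient.
- *That 17% to 78% is the plan's false-positive rate.* Those samples are false positives only for a within-caregiver claim, and only under an assumed slope of −0.6.

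It is also fair that splitting loses precision, and that when the two slopes are close the single coefficient can have the smaller error. The cortisol subset can only make precision worse. Lastly, the plan is silent on centring. Entry of the uncentred visit value is the natural reading of a concurrently measured fixed effect, but it is an inference.

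What the defence leaves open is interpretation. The exploratory label does not say what the coefficient means, and the one caveat given addresses a different problem.

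**Conclusion.** The point holds as a minor one. Followed as written, the exploratory models give a blended coefficient, which supports no statement about change in self-efficacy or cortisol going with change in outcome unless the between- and within-caregiver slopes are equal. The documents give no ground for assuming that they are.

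The size cannot be fixed from the documents. If stable levels are unrelated, nothing is lost beyond a rate close to nominal. As the between-caregiver association strengthens, the chance of an apparently clear result without any within-caregiver link rises to a third of samples in one moderate setting, and to most samples in the strongest settings tried. All of this rests on assumed ICCs and slopes, complete visits and a 5% level. The Aim 1 results and the main Aim 2b group contrasts do not use this predictor and are not affected.

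**What to change.** In the Aim 2 exploratory models and their Aim 3 reuse, replace the single predictor with two terms: the caregiver's mean over available visits, and the visit value minus that mean. Report both coefficients with confidence intervals, and base any statement about change on the within-caregiver term. Keep the existing caveat. The split removes stable differences between caregivers, but with concurrent measurement the within-term remains open to reverse causation and time-varying confounding, so it supports no mediation or causal claim.

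The cost is about two sentences in the Analytical Plan and no new data. The price is precision: the wider standard error shown above, limited power at this sample size, and possibly a larger mean squared error than the single coefficient if the two slopes turn out to be close. Reporting both terms lets the reader see whether they are.
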